## 2.5 Sample Size Consideration

Approximately 70 subjects will be screened to have at least 45 subjects who complete the study.

The primary analysis is based on the score of cervical mucus as a quantitative variable because it is expected to be the most powerful analysis based on the consistent mechanism of action of norgestrel on cervical mucus. However the justification of the sample size will not be based on the primary analysis as there is no basis provided by published data on this parameter, such as order of magnitude of the variance covariance matrix of the change from time point of reference. This is the reason why the sample size calculation will be based on proportions of women with no loss of protection.

A total sample size of 45 subjects who complete the study should allow to detect a loss of protection that would demonstrate a pertinent effect on a substantial proportion of the population. Indeed if the difference between a cycle (or day) with a perfect use and a cycle (or day) with an infringement in the schedule is 14 % in the expected proportions of women with a loss of protection at any time and if the proportion of discordances between the 2 situations is 17% then the exact power is equal to 79.1%. If the expected difference in proportions is 15% with a rate of discordance of 18% then the exact power is 82.4% for an unconditional test. The expected difference in proportions need, therefore, to reach 14-15 % to get a sufficient power for detecting a significant difference. This difference in proportions is a substantial difference knowing that most of change in status are in the same direction i.e. from protection to loss of protection.

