## 3.0 STATISTICAL METHODS

### 3.1 Statistical Handling Policy and Analysis Conventions

This section details general policies to be used for the statistical analyses. Departures from these general policies may be given in the specific detailed sections of this SAP. When this situation occurs, the rules set forth in the specific section take precedence over the general policies. The following policies will be applied to all data presentations and analyses.

- All statistical tests will use a significance level of  $\alpha = 0.05$ . Two-tailed tests will be performed for all analyses that use statistical testing.
- All p-values will be rounded to 3 decimal places. All p-values that round to 0.000 will be presented as '<0.001' and p-values that round to 1.000 will be presented as '>0.999'. Any

p-value  $\leq 0.05$  will be considered statistically significant and will be marked with one asterisk (e.g., 0.025\*).

- Summary statistics will consist of the number and percentage of responses in each category for discrete variables, and the mean, median, standard deviation (SD), minimum, and maximum for continuous variables.
- All mean values will be formatted to one more decimal place than the measured value. Standard deviation values will be formatted to two more decimal places than the measured value. Median values will be formatted to same decimal place as the measured values when that is possible without losing accuracy; otherwise, they will be formatted to one more decimal place than the measured values.
- All percentages will be rounded to one decimal place. The number and percentage of responses will be presented in the form XX (XX.X), where the percentage is in the parentheses. The denominator for percentage calculations will be the number of non-missing observations.
- All listings will be sorted for presentation in order of site number, subject number, and date of procedure or event.
- All analysis and summary tables will have the population sample size (n and % (% will not be shown in the column header if the table also presents means)) for each treatment group in the column heading.
- Calculating change from baseline to a visit will be done as follows: Change = Visit – Baseline.
- Baseline is defined as the last data point before the day of infringement (i.e. V2R-1 or V3R-1).
- Version 9.4 of SAS® or higher will be the statistical software package used to produce all summaries, listings, statistical analyses, and graphs.

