The **primary model** of interest is a mixed model for repeated measures using as response delta to  $V_{2R}$ , delta to  $V_{2R+1}$ , delta to  $V_{3R}$  and delta to  $V_{3R+1}$ . The covariates will be the period (or period effect), the intervention (type of infringement: missed pill or delayed pill), the sequence of intervention (missed pill then delayed pill and vice versa), the time (visit) and the subject. Time, period intervention type, and sequence will be considered as categorical variables. The subject as random effect (RANDOM statement of the MIXED procedure). This will permit to take into account the fact that measures from each period are derived from the same subjects. A time repeated effect (REPEATED statement of the MIXED procedure) within each combination subject\* period (SUBJECT = subject\* period as option of the

REPEATED statement). This will permit to take into account the fact that for each subject, at each period several measures are performed over time. The proper structure of the variance covariance matrix will be retained using the best fit among unstructured matrix (UN) compound symmetry (CS) and autoregressive structure (AR1).

The **primary test of interest** will be the significance of the overall mean (intercept). This will answer the question: is the overall mean change from baseline different from zero? Or does the infringement of schedule regardless the type of infringement lead to a change in mucus score?

The **contrasts or estimates of interest** are

- The effect of infringement type: does the effect of missed pill differ from the effect of 6 hours delay? If the answer is yes, then a signal of effect is detected.
- The effect of time: does the response on the day of infringement differ from the response on the day after infringement? If the answer is yes, then a signal of effect of infringement is detected.

The **primary cut-off** for full cervical mucus protection is a cervical mucus score of 4. There is, therefore, a good conception protection by cervical mucus if the cervical mucus score is  $\leq 4$ . If the cervical mucus was too thick to be collected (and thus a cervical mucus score could not be obtained) the analyses using the **FASM, ITT and PP populations** will use the following approach:

Baseline Mucus Score	Post-Baseline Mucus Score	Mucus Score Used in Analysis
0-4	Too thick to collect	Score equal to baseline
>4	Too thick to collect	Post-baseline score =4

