Too thick to collect	Any observed mucus score	Baseline score =0
Too thick to collect	Too thick to collect	Change from baseline = 0

A sensitivity analysis using the FASM population will also be done and if the cervical mucus was too thick to be collected (and thus a cervical mucus score could not be obtained) the mucus score will be assigned using multiple imputation.

The SAS code for the 2 primary contrasts of interest are:

```
PROC MIXED DATA=MUCUS;
CLASS VISIT PERIOD INTERVENTION SEQUENCE;
MODEL MUCUS_CHG = PERIOD INTERVENTION VISIT SEQUENCE / S;
RANDOM SUBJ_ID;
REPEATED / SUBJECT=SUBJ_ID*PERIOD;
ESTIMATE 'EFFECT OF INFRINGEMENT' INTERVENTION 1 -1 ;
ESTIMATE 'EFFECT OF TIME' VISIT 1 -1 1 -1;
RUN;
```

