### **Subordinated Primary Objective**

The **subordinate primary objective** is to estimate the duration of the protective effect of cervical mucus after last pill intake of norgestrel 75 mcg during reported perfect use (at the day before the infringement).

The possible increase in mucus score may have no detectable effect on conception risk depending on the level of score because it increased but remained below a threshold of good protection.

The mucus score has a value ranging from zero (not propitious for spermatozoïds progression: maximal protection) to 12 (propitious for spermatozoïds progression: minimal protection). The **primary cut-off** for full cervical mucus protection is a cervical mucus score of 4. There is, therefore, a good conception protection by cervical mucus if the cervical mucus score is  $\leq 4$ . If the cervical mucus was too thick to be collected (and thus a cervical mucus score could not be obtained) the subordinate primary objective analysis will consider the sample to have good contraception protection and have a cervical mucus score  $\leq 4$ . Otherwise if the cervical mucus score is missing the subject will not be included in the analysis for the missing endpoint.

The **responses** of interest are:

1. The full protection by cervical mucus regardless of the use of norgestrel 75 mcg if the score was and remained at 4 or below at  $V_{2R-1}$ ,  $V_{2R}$ ,  $V_{2R+1}$ ,  $V_{3R-1}$ ,  $V_{3R}$  and  $V_{3R+1}$ . The full protection by the mucus lasted for 2 x 3 days. The proportion of patients meeting this criterion is  $p_{FP}$ .
2. The absence of risk increase further to delayed intake: The score was  $\leq 4$  the day before infringement and remained at 4 or less the day of infringement and the day after the delayed pill intake. The protection by the mucus lasted at least up to the day after infringement. The proportion of patients fulfilling this criterion is  $p_{delay}$ .
3. The absence of risk increase further to missed pill: The score was  $\leq 4$  the day before infringement and remained at 4 or less the day of infringement and the day after missed pill. The protection by the mucus lasted at least up to the day after infringement. The proportion of patients fulfilling this criterion is  $p_{missed}$ .

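### Too-thick mucus is scored 0 at baseline but not afterwards, which biases the primary overall mean change upward whenever too-thick status switches between visits

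*SAP*

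**What the plan says.** The scoring table in SAP section 3.7.1 applies to the FASM, ITT and PP analyses of change in mucus score. It has four rows:

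- Baseline 0-4, later sample too thick: "Score equal to baseline", so the change is 0.
- Baseline above 4, later sample too thick: "Post-baseline score =4", so the change is 4 minus baseline.
- Baseline too thick, later score observed: "Baseline score =0", so the change is the full later score.
- Too thick at both visits: the change is 0.

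The primary test in the same section asks "is the overall mean change from baseline different from zero". Section 3.1 adds "All statistical tests will use a significance level of" 0.05, two-tailed. For too-thick samples the SAP also plans one FASM sensitivity analysis in which "the mucus score will be assigned using multiple imputation" (table 14.2.4 in section 5.5). The subordinate primary analysis follows another rule: it will "consider the sample to have good contraception protection and have a cervical mucus score" of 4 or less, whichever visit the sample comes from. Section 3.7.2.1 does the same.

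**The concern.** One physical finding receives different scores depending only on the visit at which it occurs. From a baseline in the protected range (0-4), a move to too thick can never count as a decrease. The reverse move always counts as a rise of the full observed score. Ordinary fluctuation between too thick and collectable therefore produces a positive mean change with no effect of the delayed or missed pill.

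The bias runs in the direction of the working hypothesis in section 3.7.1, that an infringement reduces protection. It affects both the primary p-value and the estimated mean change. The ITT and PP analyses use the same table, so their agreement with the FASM result would not be reassuring.

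**Working it through.** **Inputs from the SAP.** The four scoring rows and the overall-mean test (section 3.7.1); two-sided 0.05 (section 3.1); 45 completers (section 2.5); score range 0 to 12 (section 3.7.1, Subordinated Primary Objective). The SAP gives no figure for the effect of the scoring rule, so there is none to reproduce.

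**Not in the SAP, so assumed.** The too-thick rate, how persistent it is within a woman, and the score distribution. On the variance of the change, section 2.5 says "there is no basis provided by published data on this parameter".

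**Step 1: mirrored pairs.** Take no change to mean that a (baseline, post-baseline) pair is equally likely in either order. Any symmetric rule then gives mirrored pairs that sum to 0. Under the SAP rows:

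| Collectable score s | (thick, s) | (s, thick) | Sum |
|---|---|---|---|
| 0 | 0 | 0 | 0 |
| 3 | +3 | 0 | +3 |
| 4 | +4 | 0 | +4 |
| 6 | +6 | 4 - 6 = -2 | +4 |
| 12 | +12 | 4 - 12 = -8 | +4 |

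For every s from 0 to 12 the sum is min(s,4). It is never negative. With one fixed value at all visits it is 0 for every s.

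**Step 2: bias of the mean change.** Let q be the share of pairs going from too thick to collectable; under no change the same share goes the other way. Then

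bias = q × E[min(s,4)].

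With E[min(s,4)] = 2 (assumed):

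- q = 2%: 0.02 × 2 = +0.04
- q = 6%: 0.06 × 2 = +0.12
- q = 10%: 0.10 × 2 = +0.20

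If visits are independent with too-thick probability p, then q = p(1 - p). At p = 10% and scores uniform on 0-4, the bias is 0.09 × 2 = +0.18. If status never switches within a period, q = 0 and there is no bias.

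**Step 3: size of the primary test.** This was simulated under no change with 45 women, two periods, one baseline and two responses per period, complete data and 5000 runs per setting. The model had a random subject effect, compound symmetry within subject and period, and sequence, period, intervention and visit as fixed effects. The 16 settings crossed four score distributions (latent mean 2-3, SD 1.2-3, within-period correlation 0.4-0.7) with four too-thick mechanisms (independent, moderately persistent, strongly persistent, tied to low scores).

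| Too thick per visit | Bias (points) | Two-sided type I error | Median |
|---|---|---|---|
| 2% | 0.01-0.06 | 4.1-5.6% | not computed |
| 5% | 0.03-0.12 | 4.5-13.4% | 6.0% |
| 10% | 0.06-0.23 | 6.0-36.1% | 10.0% |
| 20% | 0.10-0.39 | 6.7-81.2% | 26% |
| 30% | 0.12-0.53 | 8.9-97.7% | not computed |

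One fixed value at every visit (0 or 4) gave 3.4-5.1% throughout. Under the SAP rows, the contrasts for infringement type and for time stayed at 4.2-5.7%.

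**Step 4: checks.**

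- The formula matches the simulation at 20% too thick: 0.101 × 2.00 = 0.202 against 0.200 simulated (moderately persistent), and 0.119 × 1.39 = 0.165 against 0.164 (tied to low scores).
- With status constant within a period, the bias was 0.000 and type I error 4.7%.
- A separate simulation with a t-test on each woman's mean change gave about 5-6% at 2% too thick, 7-9% at 5%, 7-20% at 10% and 11-54% at 20%. A fixed 0 or 4 gave 4.4-6.0%.

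**The case against.** Several points can be made for the plan as it stands.

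- **A woman whose mucus does not change adds no bias.** This is right: too thick at both visits scores 0, as do identical collectable scores. The bias needs status to switch within a three-day window, and "no change" here refers to the distribution over women.
- **The size is unknown.** This also stands. If too-thick mucus is rare or strongly persistent, the test stays near 5%. The direction does not depend on the rate.
- **The inflation depends on which test is run.** The SAP text names the overall mean, but its code has no ESTIMATE statement for it, and the printed intercept would be a reference-cell mean. In a simulation with 44 women, the overall-mean test rejected 7-20% at 10% too thick and 10-53% at 20%; the reference-cell intercept rejected 5-8% and 6-17%. The SAP also chooses among three covariance structures, and only compound symmetry was simulated. This qualifies the type I figures. The bias in points is unchanged, and the overall mean is the question the plan asks.
- **Multiple imputation is planned.** It bypasses the scoring table and could reveal a gap. It is a FASM sensitivity analysis only, with no model stated in the SAP, and it leaves the primary result as it is.
- **The study is exploratory, and erring toward a loss of protection is cautious.** The SAP gives no such rationale for the rule. It declares a two-sided primary test at 0.05, and a worst-case rule belongs in a labelled sensitivity analysis.
- **A total of 0 is itself an assumption.** True: thick mucus scores 0 on viscosity (section 5.3), but the other three items are not observed. A sensitivity analysis with a second fixed value addresses this.

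**Conclusion.** The concern holds. The scoring table makes the overall mean change, and hence the primary test, biased upward under no true change. Two conditions suffice: too-thick status varies within a period, and collectable scores are not all 0. Under exchangeable visits the bias is exactly q × E[min(s,4)].

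The direction is certain. The type I figures are illustrative, because they rest on assumed too-thick rates, persistence and score distributions, and on compound symmetry: close to nominal at 2% too thick, with a median of 10.0% at 10% and 26% at 20%.

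The problem is confined to the overall-mean test and the estimated mean change in the FASM, ITT and PP analyses. The infringement-type and time contrasts are not materially affected, and neither are the analyses of scores of 4 or less. Because the defect sits in the named primary test and the rate is not known in advance, it should be corrected before that analysis is run.

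**What to change.** In section 3.7.1, give a too-thick sample one value at every visit in the FASM, ITT and PP analyses. The value 0 is a natural choice, since the SAP already uses it at baseline. Add a FASM sensitivity analysis with 4 at every visit. Keep the multiple-imputation analysis, but state its model and restrict imputed values for too-thick samples to 0-4 both before and after baseline, in line with the subordinate primary analysis and section 3.7.2.1.

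This costs SAP wording, one derivation rule and one extra sensitivity table, with no new data.

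There is a price in sensitivity. Moves from collectable to too thick will count as decreases, and the bias will no longer add to a real rise. In one illustration (10% too thick, a 0.5-point rise in the latent score), rejection falls from 80% to 50%. The estimated mean change falls from 0.51 to 0.39. That difference of 0.12 equals the bias in the same setting under no change, so part of the apparent power came from the bias. Neither rule is guaranteed to recover a real change exactly, which is why the second fixed value is needed.

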### **Subordinated Primary Objective**

The **subordinate primary objective** is to estimate the duration of the protective effect of cervical mucus after last pill intake of norgestrel 75 mcg during reported perfect use (at the day before the infringement).

The possible increase in mucus score may have no detectable effect on conception risk depending on the level of score because it increased but remained below a threshold of good protection.

The mucus score has a value ranging from zero (not propitious for spermatozoïds progression: maximal protection) to 12 (propitious for spermatozoïds progression: minimal protection). The **primary cut-off** for full cervical mucus protection is a cervical mucus score of 4. There is, therefore, a good conception protection by cervical mucus if the cervical mucus score is  $\leq 4$ . If the cervical mucus was too thick to be collected (and thus a cervical mucus score could not be obtained) the subordinate primary objective analysis will consider the sample to have good contraception protection and have a cervical mucus score  $\leq 4$ . Otherwise if the cervical mucus score is missing the subject will not be included in the analysis for the missing endpoint.

The **responses** of interest are:

1. The full protection by cervical mucus regardless of the use of norgestrel 75 mcg if the score was and remained at 4 or below at  $V_{2R-1}$ ,  $V_{2R}$ ,  $V_{2R+1}$ ,  $V_{3R-1}$ ,  $V_{3R}$  and  $V_{3R+1}$ . The full protection by the mucus lasted for 2 x 3 days. The proportion of patients meeting this criterion is  $p_{FP}$ .
2. The absence of risk increase further to delayed intake: The score was  $\leq 4$  the day before infringement and remained at 4 or less the day of infringement and the day after the delayed pill intake. The protection by the mucus lasted at least up to the day after infringement. The proportion of patients fulfilling this criterion is  $p_{delay}$ .
3. The absence of risk increase further to missed pill: The score was  $\leq 4$  the day before infringement and remained at 4 or less the day of infringement and the day after missed pill. The protection by the mucus lasted at least up to the day after infringement. The proportion of patients fulfilling this criterion is  $p_{missed}$ .
4. The absence of risk increase due to infringement regardless of the type: The score was  $\leq 4$  the day before infringement and remained at 4 or less the day of infringement and the day after infringement. The protection by the mucus lasted at least up to the day after infringement. The proportion of patients fulfilling this criterion is  $p_{breach}$ .
5. The transient risk increase further to delayed intake: The score was  $\leq 4$  the day before infringement, exceeded 4 the day of infringement but came back to 4 or less the day after the delayed pill intake. The protection by the mucus was interrupted the day of infringement. The proportion of patients fulfilling this criterion is  $p_{delay,transient\ risk}$ .
6. The transient risk increase further to missed pill: The score was  $\leq 4$  the day before infringement, exceeded 4 the day of infringement but came back to 4 or less the day after the delayed pill intake, The protection by the mucus was interrupted the day of infringement. The proportion of patients fulfilling this criterion is  $p_{missed,transient\ risk}$ .

7. The prolonged risk increase further to delayed intake: The score was  $\leq 4$  the day before infringement, exceeded 4 the day of infringement and the day after the delayed pill intake. The protection by the mucus was interrupted the day of infringement and at least up to the day after. The proportion of patients fulfilling this criterion is  $p_{\text{delay, prolonged risk}}$ .

8. The prolonged risk increase further to missed pill: The score was  $\leq 4$  the day before infringement, exceeded 4 the day of infringement and the day after the missed pill. The protection by the mucus was interrupted the day of infringement and at least up to the day after. The proportion of patients fulfilling this criterion is  $p_{\text{missed, prolonged risk}}$ .

Comparison between the missed pill and the delayed pill can easily be performed and tested through a stratified McNemar test (stratification on the site, CMH option in SAS). The SAS glimmix procedure for repeated measures was not retained for decision making test because convergence issues in fitting the model are too frequent. The first null hypothesis is  $H_0$ : Proportion of protected women at baseline (R-1) is equal to the proportion of protected women after schedule infringement and more specifically at Day R (27 hours and 30 hours post treatment). The second null hypothesis (which is only performed for the missed pill arm) is the equality of proportions at baseline (R-1) and at Day R+1 (48 hours post treatment).

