## 2.4 Study Endpoints

### 2.4.1 Primary Endpoint

The primary outcomes/endpoints are the changes from baseline (BSL), where baseline is the day before the infringement. Abbreviations for visits are defined in section 3.7.1.

- Delta from BSL to V2R (Day 42±3) = Mucus score at V2R - score at V2R-1 (Day 41±3): change from baseline to 3 (delayed pill period) or 6 hour (missed pill period) after infringement
- Delta from BSL to V2R+1 (Day 43±3) = Mucus score at V2R+1 - score at V2R-1 (Day 41±3): Change from baseline to just before pill intake the day after infringement
- Delta from BSL to V3R (Day 70±3) = Mucus score at V3R - score at V3R-1 (Day 69±3): Change from baseline to 3 (delayed pill period) or 6 hour (missed pill period) after infringement
- Delta from BSL to V3R+1 (Day 71±3) = Score at V3R+1 - score at V3R-1 (Day 69±3): Change from baseline to just before pill intake the day after infringement

The subordinate primary endpoint is the proportions of subjects with “protective effect of cervical mucus” the missed pill period and the delayed pill period for the following categories:

- Full protection by cervical mucus regardless of the use of norgestrel 75 mcg
- Absence of risk increase further to delayed intake
- Absence of risk increase further to missed pill
- Absence of risk increase due to infringement regardless of the type
- Transient risk increase further to delayed intake
- Transient risk increase further to missed pill
- Prolonged risk increase further to delayed intake
- Prolonged risk increase further to missed pill

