- (m) At V11, the mucus analysis will be performed before the 1st study medication intake
- (n) Mucus analysis to be performed at T2/3R-1 +8 h ± 30 min.
- (o) Mucus analysis to be performed at T2/3TR-1 +3h ± 15 min.
- (p) Mucus analysis to be performed at T2/3R-1 +6 h ± 15 min.
- (q) Mucus analysis to be performed within 30 min before study medication intake
- (r) Blood sampling for PK analysis at D1: subjects with even study number at predose, 2 h ± 15 min, 6 h ± 15 min and 12 h ± 30 min post-treatment and subjects with odd study number at 1 h ± 15 min, 4 h ± 15 min , 8 h ± 30 min and 24 h ± 30 min post-treatment

- (s) Blood sampling for steady state during first visit in week 3: subjects with odd numbers at predose, and between 0.5 h and 2h (morning visit), and subject with even numbers between 5 h and 9 h post-treatment (afternoon visit)
- (t) Blood sampling for compliance during 1st visit of weeks 5 and 9 within 30 min of cervical mucus sampling
- (u) Blood sampling for PK analysis at  $T2/3_{R-1} + 8h \pm 30 \text{ min}$
- (v) Blood sampling for PK analysis at  $T2/3_{R-1} + 3h \pm 15 \text{ min}$ ,  $T2/3_{R-1} + 5.5h \pm 15\text{min}$ ,  $T2/3_{R-1} + 7.5h \pm 30\text{min}$
- (w) Blood sampling for PK analysis at  $T2/3_{R-1} + 6h \pm 15\text{min}$
- (x) Blood sampling for PK analysis at  $T2/3_{R-1}$  within 30 min before study medication intake
- (y) No E2, FSH and LH measurements during extra-visits after postovulatory image is observed

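### The mucus risk classes have no place for a woman still protected on the day of infringement but unprotected the day after, which matters most for the missed pill

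*SAP*

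**What the plan says.** The subordinate primary objective in SAP section 3.7.1 is to estimate how long mucus protection lasts after the last pill. The primary "cut-off for full cervical mucus protection is a cervical mucus score of 4", and a sample too thick to collect counts as protected. Eight responses are then defined on the scores at R-1, R and R+1:

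- Response 1 (full protection) applies "if the score was and remained at 4 or below at" all six visits of the two infringement periods.
- Responses 2 to 4 (absence of risk increase) need a score of 4 or less at R-1, R and R+1. For the missed pill, the score must have "remained at 4 or less the day of infringement and the day after missed pill".
- Responses 5 and 6 (transient) need protection at R-1, then a score that "exceeded 4 the day of infringement but came back to 4 or less the day after the delayed pill intake". Response 6 is the missed-pill version but carries this same reference to the delayed pill.
- Responses 7 and 8 (prolonged) need protection at R-1 and a score above 4 on both later days. For the missed pill, the score "exceeded 4 the day of infringement and the day after the missed pill".

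Section 2.4.1 lists the same eight categories, ending with "Prolonged risk increase further to missed pill". The summary table in section 2.4.2 assigns all eight to the duration objective.

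On timing, the first McNemar null hypothesis is set "more specifically at Day R (27 hours and 30 hours post treatment"). The second, for the missed pill only, compares R-1 with R+1, which the SAP places at 48 hours. Footnote (q) of the schedule in section 5.1 fixes the R+1 sample: "Mucus analysis to be performed within 30 min before study medication intake".

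**The concern.** Both risk classes are tied to a score above 4 on Day R. A woman whose score first passes 4 on Day R+1 fails the absence definition and meets neither risk definition.

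In the missed-pill period no tablet is taken between R and R+1, so R+1 is the longest pill-free interval the study measures. A woman whose protection outlasts 30 h but not 47.5 h is a case that a duration endpoint should show, and the eight categories give her no row. A reader who adds transient and prolonged to obtain the proportion losing protection after a missed pill would get a figure that is too low. It would also differ in kind from the quantity in section 2.5, which plans on loss occurring at any time.

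The delayed-intake classes have the same gap. It matters less there, because a tablet is taken between R and R+1.

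**Working it through.** **1. Hours since the last pill** (time points in section 3.7.1, schedule in section 5.1)

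| Period | R-1 | R | R+1 |
|---|---|---|---|
| Missed pill | 8 h | 24 + 6 = 30 h | 48 - 0.5 = 47.5 h, no pill since R-1 |
| Delayed pill | 8 h | 24 + 3 = 27 h | 47.5 - 30 = 17.5 h after the delayed tablet |

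This reproduces the SAP's 27 and 30 hours, and its 48 hours apart from the half hour before intake.

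**2. Patterns for a woman protected at R-1**

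| R-1 | R | R+1 | Response |
|---|---|---|---|
| ≤4 | ≤4 | ≤4 | absence (2, 3, 4) |
| ≤4 | >4 | ≤4 | transient (5, 6) |
| ≤4 | >4 | >4 | prolonged (7, 8) |
| ≤4 | ≤4 | >4 | none |

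Three of the four patterns are classified. The four patterns starting above 4 at R-1 are also unnamed, but those women had no mucus protection to lose.

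**3. What the other planned analyses see**

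- The R-1 versus R+1 McNemar test for the missed pill has as its protected-to-unprotected cell late loss plus prolonged loss. It counts late loss but cannot separate the two.
- The mixed model includes the changes to R+1 in both periods, so a late rise enters as part of a mean change, not as a count of women.

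**4. Possible size**

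The SAP gives no rate for the missing pattern. Section 2.5 gives planning values for 45 completers. With difference d and discordance ψ, the proportion changing from protected to unprotected is b = (ψ + d)/2.

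- d = 14%, ψ = 17%: b = (0.17 + 0.14)/2 = 0.155, and 45 × 0.155 = 7.0 women.
- d = 15%, ψ = 18%: b = (0.18 + 0.15)/2 = 0.165, and 45 × 0.165 = 7.4 women.

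The share of losses first seen at R+1 must be assumed. For the first scenario:

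| Assumed share first seen at R+1 | Women in no risk class |
|---|---|
| 25% | 0.25 × 6.975 = 1.7 |
| 50% | 0.50 × 6.975 = 3.5 |
| 75% | 0.75 × 6.975 = 5.2 |

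The possible range is 0 to about 7.

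As a check on the inputs, these cells with n = 45 give the SAP's stated powers of 79.1% and 82.4% (79.10% and 82.43% recomputed) under an exact unconditional test at one-sided 0.05. At two-sided 0.05 the same test gives 69.5% and 73.6%. Section 3.1 calls for two-tailed tests. That is a separate matter and does not affect the gap in the classes.

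**5. How far the assumed share can move**

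If missed-pill losses were permanent and spread evenly in time up to 47.5 h, the share falling after 30 h would depend on where the spread starts:

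- from 24 h: (47.5 - 30)/(47.5 - 24) = 17.5/23.5 = 74%
- from 8 h, the R-1 score: 17.5/(47.5 - 8) = 17.5/39.5 = 44%

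Nothing in the SAP favours either start point, or an even spread.

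**The case against.** The best defence is that late loss is not ignored. The paragraph straight after the definitions tests R-1 against R+1 for the missed pill, the mixed model has an R versus R+1 contrast, and section 3.7.2.1 takes the worst score in each period. All three respond to a late rise. The absence proportions are right too, since late-loss women are properly excluded from them. For women with all three scores, late loss can even be derived:

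late = P(≤4 at R-1) - absence - transient - prolonged

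The first term is needed anyway for the McNemar tests. The SAP also calls these responses of interest and lets responses 1 to 4 overlap, so it never promised a partition.

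Most of this stands. The gap lies in the reported classes, not in the data or in every test. It still needs closing. The McNemar cell mixes late with prolonged loss. The subtraction works only on a common denominator, while the SAP drops women with missing scores endpoint by endpoint. The proportion protected at R-1 is not one of the eight responses.

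A reader might infer that only three of eight possible patterns are covered. That counts four patterns with no protection at baseline; the fair count is three of four. A reader might also infer that the transient class for the missed pill claims recovery through resumed intake. Response 6 describes a score pattern and gives no cause. Its evident flaw is the reference to a delayed intake, apparently carried over from response 5.

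**Conclusion.** The gap is certain, because it follows from the definitions alone: a woman protected at R-1 and R and unprotected at R+1 has no risk class, for either type of infringement. For the missed pill this omits loss of protection between 30 h and about 47.5 h after the last pill from the risk classes. Transient plus prolonged therefore understates loss and does not add up to the loss at any time on which section 2.5 is planned.

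The size is not known. About 2 to 5 of 45 women is illustrative. It assumes that the section 2.5 planning values apply to the missed-pill period and that 25% to 75% of losses first appear at R+1; the possible range is 0 to 7. It is tempting to infer from the timings that most missed-pill losses, perhaps three quarters, would be late. The SAP does not support that: the figure falls from 74% to 44% when the assumed start of loss moves from 24 h to 8 h.

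This is a modest reporting defect in an exploratory study, but it affects the categories that carry one of the two primary objectives, so it should be corrected.

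**What to change.** In section 3.7.1, and in the matching lists in sections 2.4.1 and 2.4.2:

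1. Add a late-onset risk increase response for each infringement type: 4 or less at R-1 and R, above 4 at R+1.
2. Report the number not protected at R-1 in each infringement period. Absence, transient, prolonged and late-onset should then account for every woman protected at R-1 with complete scores.
3. Correct response 6 so that it refers to the missed pill, and note that in this period no pill is taken between the R and R+1 scores.

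The cost is SAP wording and a few extra table rows. All the scores are already scheduled, so no new data are needed.
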